All researchers and clinicians taking part in this study will conduct all practices in compliance with this protocol, proceed under Good Clinical Practice (GCP), and follow all regulatory requirements outlined by University, State, and Federal agencies.

2.5 Description of the population to be studied:

When examining the impact of an agent that acts on inflammation and has antioxidant properties, targeting neuroprotection, it is important to identify and treat patients at the earliest stage. Therefore, we propose to investigate the effects of elderberry juice in patients with mild cognitive impairment, MCI. MCI is characterized by impaired memory and preserved activities of daily living (6,7). Patients with this diagnosis are at significantly increased risk for developing dementia (8-10). Most researchers propose MCI as the mildest endpoint on the spectrum of Alzheimer's disease (9). With the recent advances in treatment options for Alzheimer's disease, much attention has been directed at intervention at earlier stages. Recent research has focused on whether or not agents may delay the progression from MCI to dementia (11, 12). In addition to any delay in or prevention of progression, it would also be of interest to determine whether agents result in any cognitive benefits for MCI patients. Studies have examined to effects of cholinesterase inhibitors, the first type of drug on the market for Alzheimer's disease, on cognition and global assessment outcomes in MCI, and have revealed effects on global assessment, psychomotor speed, and attention, but not on specific memory tasks (13).

Inclusion criteria: CDR score of 0.5 and an MMSE of at least 24, as well as have no known sensitivity to elderberry products, or presence of any health condition that in the clinical experience of the investigators might impair their ability to complete the study. Recruited subjects will be aged 50 or more.

Exclusion criteria: Known history of sensitivity to elderberry products. Known allergy to honeysuckle. Current diagnosis of diabetes. Bleeding disorder. Currently pregnant. Currently making changes to other drugs that might affect cognitive performance (subjects showing the greatest cognitive decline and other signs of Alzheimer's disease may be prescribed cholinesterase inhibitors as this is a standard of care for Alzheimer's disease but not MCI). Presence of any condition the health professional believes will impair ability to complete

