Our aim is to begin to explore the potential translational impact of elderberry juice, a botanical agent. To achieve this, we will perform a pilot trial of elderberry juice in patients with mild cognitive impairment (MCI). It is critical to determine whether the course of development of Alzheimer's can be altered in this high-risk population. Our primary outcome measure will be visuospatial problem solving, as this has been shown to be sensitive to drug effects in MCI. We will also track other cognitive outcomes as well as the incidence of progression to dementia. Furthermore, we will examine inflammatory markers to begin to explore the potential mechanism of its effect. The results of this study will yield pilot data for publication and for development of a larger clinical trial for which external funds will be sought.

4. Trial Design

4.1 A specific statement of the primary endpoints:

Subjects will be assessed for changes in cognitive performance measures: CDR (for determination of progression to dementia), MMSE (general cognition), IADL (functional ability), HVLT (memory), BNT (language), Rey CFT (spatial function), anagrams (verbal cognitive flexibility), and VPS (spatial cognitive flexibility).

4.2 A description of the type/design of trial:

Double-blinded placebo-controlled pilot trial

4.3 A description of the measures taken to minimize/avoid bias:

Twenty of the subjects will be randomly assigned to receive elderberry juice and twenty control subjects will be randomly assigned to receive an equal amount of a flavored liquid with no nutritional content as a placebo control group. The clinicians will be blinded as to group, as will be the assessor. [name], a graduate student in [name] lab who is otherwise uninvolved in the study, will keep the unblinding code in case a need arises to break the code for clinical purposes or preliminary data analyses.

4.4 A description of the trial treatment(s) and the dosage and dosage regimen of the investigational product(s):

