In other research examining the effects of other anthocyanin-rich fruit extracts on MCI, a significant effect was revealed on word list memory with 12 subjects (33). In this study, the subjects in the treatment group improved their word list memory scores from 35.2 to 38.6, with a

standard deviation of less than 2. Based upon this data, the power of a study at the level of $\alpha=0.008$ (adjusted for multiple measures for the various cognitive tasks) with a sample of 13 would be 0.95 for detecting an effect of elderberry juice if it has similar effects as the grape juice on memory, and a sample of 18 would yield a power of 0.99. Therefore, we expect that the sample size of 20 per group (total 40) would be sufficient to reveal effects on word list memory (HVLT), as well as our other cognitive and behavioral outcome measures (VPS, MMSE, Rey CFT, BNT, and IADL), if their performance follows the same response as observed with word list memory. This pilot study will also yield results for the purpose of deriving power calculations for determination of appropriate sample sizes for larger, subsequent studies.

[name] and [name] see at least 80 patients with MCI each year in their clinics. Most of these patients have expressed a willingness to participate in research. We may need to enroll up to 60 subjects to obtain a sufficient set of 40.

6.3 The selection of subjects to be included in the analyses:

Subjects taking less than 75% of the scheduled dose or failing to complete at least one follow-up session will be excluded from analysis.

7. Potential Risks Related to Drug

The elderberry can cause problems for people with a known allergy in the *Caprifoliaceae* family (honeysuckle). The related side effects are given below.

- There are reports of gastrointestinal distress, diarrhea, vomiting, abdominal cramps, and weakness after drinking elderberry juice made from crushed leaves, stems, and uncooked elderberries. **Notably, toxicity typically arises from uncooked berries and preparations for this study will be carried out to minimize such reactions.**
- In theory, high doses or long-term use of elder flowers may have diuretic (urine-producing) effects. People taking diuretics or drugs that interact with diuretics should use caution when taking products containing elder.
- Elder may also lower blood sugar levels. Dizziness, headache, convulsions, and rapid heart rate have also been reported.

8. Data Handling and Recordkeeping

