Updated 04/28/2020

Statistical Analysis Plan

Identifier: NCT02414607

Study Title: Effect of Elderberry Juice on Cognition and Inflammation in Patients With Mild Cognitive Impairment

Baseline demographics and clinical characteristics

Group differences between Elderberry and Placebo control were evaluated using independent sample t-tests for continuous variables and chi-square analyses for categorical variables.

Cognitive Measures

For each outcome variable, fixed effects of group (Elderberry, Placebo control), time (baseline, 3-month follow-up; baseline, 6-month follow-up) and the group by time interaction will be tested using Multilevel Modeling (MLM) analyses in SPSS (version 27), using a first-order Autoregressive covariance structure (AR1) and restricted maximum likelihood estimation. Given the preliminary nature of the study, pairwise comparisons between groups and within groups over time will be examined for both significant effects ($\alpha \leq .05$) and trends ($\alpha < .10$).

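### VPS is the primary outcome in protocol section 3, but 4.1, the sample size in 6.2 and the SAP do not carry it through, and the SAP drops the 0.008 level used in 6.2

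*SAP*

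**What the plan says.** - **Protocol section 3** ranks the outcomes: "Our primary outcome measure will be visuospatial problem solving, as this has been shown to be sensitive to drug effects in MCI". The rest come second: "We will also track other cognitive outcomes as well as the incidence of progression to dementia".
- **Protocol 4.1**, whose heading announces the primary endpoints, begins "Subjects will be assessed for changes in cognitive performance measures: CDR (for determination of progression to dementia), MMSE (general cognition" and continues to eight measures: CDR, MMSE, IADL, HVLT, BNT, Rey CFT, anagrams and VPS. It gives no ranking, visit or multiplicity rule.
- **Protocol 6.2** takes a change of 35.2 to 38.6 on word-list memory, SD under 2, from the treatment group of a cited grape juice study. It states power at alpha 0.008, "adjusted for multiple measures for the various cognitive tasks) with a sample of 13 would be 0.95", and 0.99 with a sample of 18. It concludes that 20 per group suffices for HVLT and extends this to "our other cognitive and behavioral outcome measures (VPS, MMSE, Rey CFT, BNT, and IADL), if their performance follows the same response". That makes six measures. CDR and anagrams are not among them.
- **SAP, Cognitive Measures**, treats all outcomes alike: "For each outcome variable, fixed effects of group (Elderberry, Placebo control), time (baseline, 3-month follow-up; baseline, 6-month follow-up"), plus the group-by-time interaction. The thresholds follow: "Given the preliminary nature of the study, pairwise comparisons between groups and within groups over time will be examined for both significant effects" at .05, with trends read below .10. It does not list the outcomes, name a primary outcome or visit, mention 0.008, or give a level for the interaction.

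**The concern.** The protocol itself judged that several cognitive measures called for an adjusted alpha, and it presented the sample size on that footing. The SAP keeps neither the adjustment nor the ranking in section 3. Its only stated reason is that the study is preliminary.

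Someone working from the SAP cannot tell which outcome, which of two visits, or which contrast (group by time, groups at follow-up, or change within a group) decides the result. Section 3 says the results are meant for publication and for planning a larger trial, so a finding picked by chance from many could be carried forward.

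**Working it through.** **1. The plan's own power figures.** Inputs from 6.2: difference 38.6 - 35.2 = 3.4; SD 2 (upper limit of the stated value); alpha 0.008. Assumed: two-sided test, normal approximation, samples of 13 and 18 read as per arm.

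Power = Φ(d·√(n/2) - z), with d = 3.4/2 = 1.7 and z = 2.652.
- n = 13: 1.7 × √6.5 = 4.334; 4.334 - 2.652 = 1.682; power 0.954 (stated 0.95).
- n = 18: 1.7 × √9 = 5.100; 5.100 - 2.652 = 2.448; power 0.993 (stated 0.99).

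The figures reproduce. They describe word-list memory in another study, and they use a within-arm change as if it were a difference between groups.

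**2. Where 0.008 comes from.** 0.05/6 = 0.0083, which fits the six measures in 6.2. Eight measures would give 0.05/8 = 0.00625. For six independent tests, the chance of at least one false positive is 1 - 0.992^6 = 4.7% at 0.008 and 1 - 0.95^6 = 26.5% at .05.

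**3. False-positive chance under the SAP.** Null simulation with 20 per arm and three visits with first-order autoregressive correlation 0.6, using two-sided t-tests between groups on change from baseline. With complete data and one baseline/follow-up pair per model, the group-by-time test in the SAP's model equals this t-test.

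*VPS only, both visits, .05:* about 8.6%, and between 8.4% and 8.7% for visit correlation 0.5 to 0.8. If the visits were independent: 1 - 0.95² = 9.75%.

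*Any of seven measures.* The seven are those in 4.1 without CDR. CDR is left out of the simulation because entry fixes it ("Inclusion criteria: CDR score of 0.5 and an MMSE of at least 24"), so it has no baseline spread. Ranges run from between-outcome correlation 0.7 to 0:

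| Level | One visit | Two visits |
|---|---|---|
| .05 | 18-30% | 29-47% |
| 0.008 | 4-6% | 7-10% |
| .10 (trend) | 32-52% | 49-72% |

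Check at independence, one visit: 1 - 0.95^7 = 30.2%; 1 - 0.992^7 = 5.5%; 1 - 0.90^7 = 52.2%. The documents give none of these correlations. The count of outcomes is from 4.1 because the SAP lists none. Within-group comparisons and the CGIC, which is rated at each follow-up visit, are not counted.

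**4. What 20 per arm can detect.** Noncentral t, 38 df, 80% power: 0.91 SD of the change score at .05 and 1.16 SD at 0.008. The larger alpha needs the smaller difference, so moving from 0.008 to .05 raises power.

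**The case against.** **A primary outcome exists.** Section 3 names VPS and places the others behind it. The heading of 4.1 reads like a template prompt, the text beneath does not call the eight measures primary, and the SAP does not contradict section 3. This stands in large part. It leaves the primary visit and contrast unnamed, and neither 4.1 nor the SAP repeats the choice.

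**The rates over seven measures answer another question.** If VPS governs, the relevant inflation is the 9% for two visits. This also stands. The larger rates apply only if any measure may be called positive, which the SAP's wording allows but does not require.

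**It is a pilot with open thresholds.** That justifies exploratory reading and lowers the severity. It does not reconcile the four places.

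**The documents contain VPS evidence.** The background reports p = 0.038 for VPS change at one year in 22 subjects. Assuming a two-sided t-test (t = 2.22, 20 df) and group splits from 11/11 to 6/16, neither of which is stated, d is about 0.95 to 1.06, and 20 per arm would have 83-91% power at .05. This is one small result at a visit that the SAP does not analyse, so it is probably optimistic. It does bear on 6.2.

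**Stronger readings to avoid.** A reader might infer that the trial has no primary outcome; section 3 says otherwise. A reader might infer that dropping 0.008 leaves the trial too small; testing at .05 does the reverse. A reader might infer that the outcome was chosen after results were seen. The SAP does describe the baseline comparisons in the past tense, and 4.3 and 4.6 let the code be broken for preliminary analyses, but neither shows that this happened.

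**Conclusion.** The point holds as a fault of consistency and reporting that should be fixed. Section 3, section 4.1, section 6.2 and the SAP give four different accounts of what is primary and at what level it is tested. The adjusted alpha in 6.2 has no counterpart in the analysis.

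The size depends on which text governs: about 9% instead of 5% under section 3, or 18-30% (one visit) to 29-47% (two visits) if any of seven measures may be declared positive at .05. A single VPS test at one pre-named visit would keep 5%. The sample size is not undermined by the change of alpha, but its stated justification is borrowed for VPS: 6.2 gives no VPS effect size or SD and assumes that VPS responds as word-list memory did.

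**What to change.** 1. **In 4.1 and the SAP**, name VPS as the single primary outcome, at one of the SAP's two visits, with the group-by-time contrast tested once at two-sided .05. The documents do not settle the visit: the 12-week rationale in 2.3 comes from other fruit preparations, and the only reported VPS effect was at one year. If unblinded results have already been seen, say that the choice was made afterwards.
2. **Label as exploratory** all other outcomes (including CDR and CGIC), the other visit and the within-group comparisons. Report 95% confidence intervals and do not count trends as positive results. If any of these is to be called significant, use an alpha adjusted for the actual number of tests. A formal gatekeeping scheme is optional in a pilot.
3. **In 6.2**, state that the power figures come from word-list memory in the cited grape juice study at 0.008 and are extrapolated to HVLT and the other measures. State that no VPS effect size or SD is given, only p = 0.038 at one year in 22 subjects, and that 20 per arm gives 80% power for about 0.91 SD of the VPS change score at .05.

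**Cost:** wording only, with no extra patients or data. Fewer results can be called positive. Blind prespecification may no longer be possible, in which case only transparent labelling remains.

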subjects with MCI were recruited for our study with a Clinical Dementia Rating (CDR) (22,23) score of 0.5, and a Folstein Mini Mental Status Examination (MMSE) (24) score of at least 24. At the first visit, all subjects were given the MMSE in order to assess global function across several domains including memory, and the Hopkins Verbal Learning Test (25) to assess verbal memory, as well as non-memory tasks including the Boston Naming Test (BNT) (26) (primarily considered as assessing language (naming)), Rey Complex Figure copying (Rey CFT) (27-29) (primarily considered as assessing visuospatial ability), a series of anagrams (primarily considered as assessing verbal and divergent cognitive flexibility) (30) (Rearrange these letters to form an English word: OGRF, RDWO, FALC, LANI, MHBTU, HTRSI, DSLEI, TMLAE), and the visuospatial problem solving battery (VPS) adapted from the “matchstick” problems (15, 31). As with our previous work with these types of tasks (14,30), solution latencies were recorded for performance on both. There was no significant difference between the two groups at baseline. However, at one year, the treated group performed significantly better on their change scores than the not treated group for the VPS task ($p=0.038$). Of interest, there were also trends detected for better change scores in the treated group for the Rey CFT, BNT, anagrams, and importantly, the IADL. As with previous research (13), no effect was observed on the memory task, the HVLТ (paper in preparation). We wish to determine the potential effects of elderberry juice on preserving cognitive functioning in a group of people at risk for cognitive impairments in the future.

2.3 Description of and justification for the route of administration, dosage, dosage regimen, and treatment period(s):

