Subjects will drink 5 ml juice by mouth, diluted in 8oz of water, three times daily. Subjects will be given sufficient juice at each visit to last until the next visit. Juice containers will be clearly labeled indicating the contents as a research supplement with directions advising subjects of dose schedule. Subjects and caregivers will also be asked to check each dose on a dose log (indicating day of trial, date, time, and dose), and will bring the juice containers to the next visit to confirm that a proper amount has been administered.

4.5 Subject Involvement:

Prior to initiation of elderberry juice or placebo, baseline visit 1, subjects will be assessed with the CDR (for determination of progression to dementia), MMSE (general cognition), IADL (functional ability), HVL (memory), BNT (language), Rey CFT (spatial function), anagrams (verbal cognitive flexibility), and VPS (spatial cognitive flexibility). They will also be administered a Food Frequency Questionnaire to determine any individual differences in diet that might be relevant to the current study's findings. After initiation of elderberry juice or control, subjects will be retested at 12 weeks, visit 2, (the timeframe that revealed significant effects with other anthocyanin-rich fruit preparations (33,34), 6 months, visit 3, and (pending resubmission for second year of support) 12 months, visit 4. At each visit following baseline the Clinical Global Impression of Change (CGIC) will also be administered. Blood samples (30mL) will be obtained at baseline and each time point in the trial to determine immunological markers, 4 times total if subject progresses through all time points.

4.6 Maintenance of trial treatment randomization codes:

The clinicians will be blinded as to group, as will be the assessor. [name], a graduate student in [name] lab who is otherwise uninvolved in the study, will keep the unblinding code in case a need arises to break the code for clinical purposes or preliminary data analyses. This will be securely stored in her lab space at [name]. All subject data will be coded to a study specific code and all identifying information will be stored on a separate secure server.

6.2 The number of subjects planned to be enrolled and reason for choice of sample size:

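### The SAP screens within-arm and between-arm pairwise comparisons beside a valid group-by-time test, does not say which result decides, and states no baseline adjustment

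*SAP*

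**What the plan says.** The SAP, under Cognitive Measures, fits one type of mixed model to every outcome variable. Group and time are fixed effects, and "the group by time interaction will be tested using Multilevel Modeling (MLM) analyses in SPSS (version 27"), with AR(1) covariance and REML. Baseline enters as a level of time, paired with the 3-month and the 6-month follow-up. No baseline covariate and no common baseline mean is stated. Citing the study's preliminary character, the SAP adds that "pairwise comparisons between groups and within groups over time will be examined for both significant effects" at 0.05 and for trends below 0.10. It names no primary outcome, deciding contrast or deciding visit, and does not make the pairwise comparisons depend on the interaction.

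The protocol does not settle this:

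- Section 3: "Our primary outcome measure will be visuospatial problem solving" (VPS).
- Section 4.1, headed as the statement of primary endpoints: "Subjects will be assessed for changes in cognitive performance measures: CDR (for determination of progression to dementia"), followed by MMSE, IADL, HVLT, BNT, Rey CFT, anagrams and VPS, eight measures in all.
- Section 6.2 bases power on word list memory at alpha 0.008, a level the SAP does not carry over.
- No section names 3 or 6 months as the deciding visit.

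The background text ahead of section 2.3 shows that the investigators have used a between-arm comparison of change before: "the treated group performed significantly better on their change scores than the not treated group for the VPS task".

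**The concern.** The interaction compares change between randomised arms. A within-arm comparison does not: it combines any juice effect with practice, drift and regression to the mean. If elderberry changes significantly and placebo does not, the two changes may still be nearly equal. The SAP leaves open that such a result, or a trend at 0.10, is reported as an effect on any of several outcomes at either visit. Section 3 says the results are meant for publication and for developing a larger trial, so a misleading signal has consequences.

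The second and smaller issue is precision. With baseline only a level of time and a free group effect, the interaction is a change-score comparison. Between-arm pairwise comparisons at a follow-up visit do not use baseline at all. Baseline adjustment uses data already collected and is usually more precise than either.

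**Working it through.** **1. The plan's own figure.** Section 6.2 takes a rise from 35.2 to 38.6 (3.4 points) in a treated group, with SD below 2 (2 used), alpha 0.008. Two-sided normal approximation, n per arm: power = Φ(3.4/(2√(2/n)) − 2.652).

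- n = 13: Φ(4.334 − 2.652) = 0.954 (stated 0.95).
- n = 18: Φ(5.100 − 2.652) = 0.993 (stated 0.99).

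The figures reproduce. The input, however, is a within-arm change used as if it were a between-arm difference, which is the reading at issue here.

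**2. How often one arm alone is significant with no juice effect.** Assumptions, none from the documents except 20 per arm: complete data, roughly normal scores, and the same gain g (in SDs of change) in both arms. With pooled SD and 38 df, each arm is significant with probability p ≈ Φ(g√20 − 2.024) for g well above 0, and p = 0.05 at g = 0. Treating the arms as independent, the pattern has probability p(1 − p).

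- g = 0: 0.05 × 0.95 = 0.048.
- g = 0.3: p = Φ(1.342 − 2.024) = 0.248, so p(1 − p) = 0.186.
- g = 0.45: p = Φ(2.012 − 2.024) = 0.495, so p(1 − p) = 0.250. The simulated rate is slightly lower because the arms share the pooled SD.

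Simulation, 400,000 draws:

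| Gain (SD of change) | Pattern at 0.05 | Of these, interaction not significant | Pattern at 0.10 |
|---|---|---|---|
| 0 | 4.7% | 66% | 8.8% |
| 0.1 | 6.6% | 74% | 11.3% |
| 0.3 | 18.6% | 88% | 22.9% |
| 0.4 | 23.5% | 90% | 24.1% |
| 0.45 | 24.3% | 90% | 22.7% |
| 0.6 | 18.6% | 89% | 13.3% |
| 0.8 | 5.9% | 80% | 2.9% |
| 1.0 | 0.8% | 62% | 0.3% |

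Counting improvement only, the no-gain rate is 2.4% at 0.05 and 4.4% at 0.10.

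Cross-check with separate arm SDs and a gain of 0.3 SD of the score. At correlation 0.5 the SD of change is √(2 × 0.5) = 1, so the gain is 0.30 SD of change and the pattern rate is 19%. At correlation 0.8 the SD of change is √0.4 = 0.632, so the gain is 0.47 and the rate is 25%. The interaction test stays at 5%.

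**3. Number of routes.** With eight outcomes, two visits, no effect and an assumed between-outcome correlation of 0.4, at least one interaction contrast is significant in 42% to 45% of trials at 0.05 and in 66% to 69% at 0.10. Adding follow-up between-arm and within-elderberry comparisons, with no practice gain, gives 75% to 77% and 93% to 95%.

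**4. Precision.** Let r be the baseline to follow-up correlation, which the documents do not give. In units of the score variance:

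- interaction (change score): 2(1 − r);
- raw follow-up comparison: 1;
- baseline-adjusted: (1 − r²)(1 + 1/36), the last factor being the cost of estimating the slope with 20 per arm.

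Adjusted over interaction is therefore (1 + r)/2 × 37/36. The table assumes a true difference of 0.7 SD for power (60,000 trials).

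| r | Variance ratio to interaction | Variance cut against interaction | Equivalent n per arm (20/ratio) | Cut against raw follow-up | Power, interaction / adjusted | Same, 15 per arm |
|---|---|---|---|---|---|---|
| 0.5 | 0.771 | 23% | 26 | 23% | 58 / 69% | 46 / 55% |
| 0.7 | 0.874 | 13% | 23 | 48% | 80 / 85% | 66 / 72% |
| 0.8 | 0.925 | 8% | 22 | 63% | 93 / 94% | 83 / 86% |
| 0.9 | 0.976 | 2% | 20.5 | 80% | 99.8 / 99.8% | 98.5 / 98.6% |

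Type I error was 0.049 to 0.051 for all three analyses. In one simulated two-visit data set the interaction and the change-score t-test both gave t = −1.293. The standard error was 0.254 for the interaction, 0.237 with a common baseline mean and 0.233 with a baseline covariate. If the scores were skewed latencies analysed untransformed (assumed lognormal, log-SD 0.5), the cut against the interaction would be 26 / 17 / 12 / 8%.

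**The case against.** **The pairwise tests are probably follow-ups to the interaction.** Listed straight after it, that is their natural reading, and in the earlier MCI study both the significant result and the trends were between-arm. This is fair as to intent, but the text neither conditions them on the interaction nor says that it decides.

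**It is a declared pilot.** That justifies exploratory breadth and low power. It does not turn an uncontrolled change into evidence of a difference.

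**The size rests on an assumed practice gain.** This stands: the rate runs from 0.8% to 24%. With no gain, improvement in elderberry alone with a non-significant interaction occurs in only about 1.5% of trials. Under shared decline, plausible in MCI, the improvement pattern nearly vanishes (0.8% at −0.1). By symmetry, though, the mirror pattern (placebo declines significantly, elderberry does not) then arises at the tabulated rates.

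**Baseline is already used.** This is correct for the interaction, and the extra gain is slight at high r. Setting (1 + r)/2 × 37/36 = 1 gives r = 72/37 − 1 = 0.946, above which adjustment with an estimated slope gains nothing. The larger cuts apply only to raw follow-up comparisons.

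**The model could have three time levels.** The interaction would then be a 2-df test, which the power figures do not cover. With balanced data each visit's contrast is still a change-score difference.

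**Scores may not be normal, and latencies may not be analysed.** Both are possible. MMSE has an entry floor and IADL is largely preserved in MCI, and the protocol mentions latencies only for the earlier study. The figures are illustrative.

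**Section 3 does name VPS.** It does, but section 4.1 lists eight measures and the SAP is silent. The 0.008 level in section 6.2 adds a further open question about the threshold.

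**It may be late.** The SAP describes the baseline comparisons in the past tense, so analysis may have begun. If so, naming the outcome and visit now is not prespecification and must be reported as such.

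**Conclusion.** The concern holds, as an improvement available at almost no cost; the planned interaction test itself is valid. The main point is that uncontrolled within-arm results stand beside it with significance and trend labels and nothing says which decides. With no juice effect and 20 per arm, elderberry alone reaches 0.05 in 4.7% of trials without a shared gain and in at most about 24%, at a gain of 0.45 SD of change. At that peak, 0.243 × 0.90 = 22% of all trials would show the pattern without support from the interaction. These rates are per outcome and visit and depend on the assumed gain.

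The precision point is secondary. Against the interaction, adjustment saves 23% of variance at r = 0.5 and 2% at r = 0.9, with r assumed. It does not repair any imbalance from the section 6.3 exclusions, under which subjects below 75% of scheduled dose or "failing to complete at least one follow-up session will be excluded from analysis".

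**What to change.** In the SAP:

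1. For the continuous measures taken at baseline (VPS, MMSE, IADL, HVLT, BNT, Rey CFT, anagrams), judge efficacy by the baseline-adjusted between-arm contrast at follow-up. Either constrain the baseline mean to be common in the mixed model (drop the group effect at baseline) or model follow-up scores with baseline as a covariate.
2. Name the deciding outcome and the deciding visit (3 or 6 months), and the significance level that applies. Reconcile section 3 (VPS) with section 4.1 (eight measures), and the 0.008 of section 6.2 with the SAP's 0.05 and 0.10.
3. Report within-arm changes with confidence intervals, as description, without significance or trend labels.
4. Compare global CDR and CGIC between arms without baseline adjustment. Entry requires "CDR score of 0.5 and an MMSE of at least 24", so global CDR does not vary at baseline, and CGIC has no baseline score: "At each visit following baseline the Clinical Global Impression of Change (CGIC) will also be administered".
5. Date the change and state whether any unblinded results had been seen.

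Cost: SAP wording and one model line. No new data are needed.
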